4.3.2.3.6 Medically-Attended Adverse Events (MAAEs)

MAAE information will be collected throughout the study. MAAEs that occur from Visit 1 (D0) to Visit 2 (D30[+14days]) will be recorded as unsolicited AEs on the diary card as part of all unsolicited AEs collected for this post-vaccination period. MAAEs that occur from Visit 2 (D30 [+14 days]) to D180 (+14 days) will be recorded as such in the MA. An MAAE that occurs within the study period but meets the definition of an SAE should be reported only on the SAE Reporting Form, but not on the MAAE page of the CRF. The Investigator will assess the causal relationship between the MAAE and the investigational or study product as either “not related” or “Related,” as described in [Section 4.3.2.3.7](#).

4.3.2.3.7 Assessment of Causality

The Investigator will assess the *causal relationship* between each unsolicited systemic AE and vaccination as either not related or related, based on the following definitions^a:

^a ICH Guidelines, Clinical Safety Data Management E2A

0: Not related – The AE is clearly / most probably caused by other etiologies such as subject’s underlying condition, therapeutic intervention, or concomitant therapy; or the delay between vaccination and the onset of the AE is incompatible with a causal relationship; or the AE started before the vaccination (screening phase, if applicable)

1: Related – There is a “reasonable possibility” that the AE was caused by the vaccination, meaning that there is evidence or arguments to suggest a causal relationship

Note: By convention, all injection site AEs (solicited and unsolicited) and all solicited systemic reactions are considered to be related to vaccination and referred to as reactions, and therefore do not require the Investigator’s opinion on relatedness.

AEs likely to be related to the product, whether serious or not, that persist at the end of the trial will be followed up by the Investigator until their complete disappearance or the stabilization of the subject’s condition. The Investigator will inform the Sponsor of the date of final disappearance of the event.

4.4 Derived Endpoints: Calculation Methods

4.4.1 Immunogenicity

4.4.1.1 Values for Analysis

In order to appropriately manage extreme values ($< \text{LLOQ}$ and \geq upper limit of quantitation [ULOQ]) for analysis purposes, the following computational rule is applied to the values provided in the clinical database for each blood sample drawn:

- If a value is $< \text{LLOQ}$, then use the computed value $\text{LLOQ}/2$
- If a value is between $\geq \text{LLOQ}$ and $< \text{ULOQ}$, then use the value
- If a value is $\geq \text{ULOQ}$, then use the computed value ULOQ

4.4.1.2 Seroprotection

Not applicable

4.4.1.3 Fold-rise

The derived endpoint fold-rise is driven by both baseline and post-baseline computed values and is computed as follows. Generally, for extreme values, this algorithm minimizes the numerator and maximizes the denominator.

- If the baseline computed value is $< \text{LLOQ}$ and the post-baseline computed value is $< \text{LLOQ}$, then the fold-rise is 1
- If the baseline computed value is $\geq \text{LLOQ}$ and the post-baseline computed value is $\geq \text{LLOQ}$, then the fold-rise is post-baseline computed value / baseline computed value

- If the baseline computed value is \geq LLOQ and the post-baseline computed value is $<$ LLOQ, then the fold-rise is $(\text{LLOQ}/2) / \text{baseline computed value}$
- If the baseline computed value is $<$ LLOQ and the post-baseline computed value is \geq LLOQ, then the fold-rise is $\text{post-baseline computed value} / \text{LLOQ}$

Note: If baseline or post-baseline is missing, then fold-rise is missing.-

4.4.1.4 A, C, Y, W Seroresponse

hSBA vaccine seroresponse for serogroups A, C, Y, and W is defined as:

- For a subject with a pre-vaccination titer $<$ 1:8, the post-vaccination titer must be \geq 1:16.
- For a subject with a pre-vaccination titer \geq 1:8, the post-vaccination titer must be at least 4-fold greater than the pre-vaccination titer.

rSBA vaccine seroresponse for serogroups A, C, Y, and W is defined as:

- rSBA vaccine seroresponse is defined as a post-vaccination titer \geq 1:32 for subjects with pre-vaccination rSBA titer $<$ 1:8, or a post-vaccination titer \geq 4 times the pre-vaccination titer for subjects with pre-vaccination rSBA titer \geq 1:8

4.4.2 Safety

4.4.2.1 Solicited Reactions

4.4.2.1.1 Daily Intensity

All daily records for solicited reactions will be derived into daily intensity according to the following classification: None, Grade 1, Grade 2, Grade 3, or Missing.

For the derivation of daily intensities the following sequential steps will be applied:

- 1) Solicited reactions (except Fever/Pyrexia) with an investigator presence recorded as “No” and with all daily records missing then all daily intensities will be derived as None.
- 2) For a temperature partially missing after decimal point, the data will be analyzed replacing “MD” (missing data) by zero. For example, a “39.MD” daily temperature will be considered as “39.0°C” at the time of analysis.
- 3) For non-measurable solicited reactions, daily intensities will correspond to daily records reported in the clinical database. For measurable solicited reactions the daily measurements reported in the clinical database will be converted based upon the intensity scales defined in the protocol; this assumes a reaction that is too large to measure (non-measurable, “NM”) is Grade 3. Note the intensity could be considered “None” (not a reaction) in the analysis despite being considered a reaction by the investigator (e.g., swelling measurement $>$ 0 mm but $<$ 25 mm).

Note: The maximum intensity on the ongoing period is derived from the record of the maximum intensity/measurement after the end of the solicited period following the rule described above.

4.4.2.1.2 Maximum Overall Intensity

Maximum overall intensity is derived from the daily intensities computed as described in [Section 4.4.2.1.1](#) and is calculated as the maximum of the daily intensities over the period considered.

4.4.2.1.3 Presence

Presence is derived from the maximum overall intensity on the period considered:

- None: No presence
- Grade 1, Grade 2, or Grade 3: Presence
- Missing: Missing presence

Subjects with at least 1 non-missing presence for a specific endpoint will be included in the analysis. Conversely, those without a non-missing presence will not be included in the analysis of the endpoint.

4.4.2.1.4 Time of Onset

Time of onset is derived from the daily intensities computed as described in [Section 4.4.2.1.1](#). It corresponds to the first day with intensity of Grade 1, Grade 2, or Grade 3.

Note: If a reaction is not continuous (i.e., reaction occurs over two separate periods of time intervened by at least one daily intensity Missing or None) then the time of onset is the first day of the first occurrence.

4.4.2.1.5 Number of Days of Occurrence

Number of days of occurrence over the period considered is derived from the daily intensities computed as described in [Section 4.4.2.1.1](#). It corresponds to the number of days with daily intensities of Grade 1, Grade 2, or Grade 3. Number of days of occurrence on the solicited period with a specified intensity may also be derived.

4.4.2.1.6 Overall Number of Days of Occurrence

If a reaction is ongoing at the end of the solicited period, then the overall number of days of occurrence is derived from the daily intensities and the stop date of the reaction after the end of the solicited period. The overall number of days of occurrence is:

- $(\text{stop date} - \text{last vaccination date}) + (\text{number of days of occurrence within the solicited period}) - \text{length of the solicited period} + 1$

If the stop date is missing or incomplete (contains missing data [MD]), the overall number of days of occurrence will be considered as Missing.

4.4.2.1.7 Ongoing

Ongoing is derived from the last daily intensity of the solicited period computed as described in [Section 4.4.2.1.1](#) and the maximum intensity on the ongoing period. The investigator's ongoing flag is not used because the measurement would determine the ongoing status of the reaction.

If the last daily intensity of the solicited period is at least Grade 1 and maximum intensity on the ongoing period is also at least Grade 1, then the reaction is considered ongoing. In any other cases the reaction will not be considered as ongoing.

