5.3.1.4 Intensity

For solicited reactions, missing intensities will be handled as described in [Section 4.4.2.1.1](#). For unsolicited non-serious AEs, missing intensities will remain missing and will not be imputed.

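### SAP 4.4.2.1.7 calls a reaction graded on D7 not ongoing when its post-D7 maximum intensity is Missing, even with a complete stop date after D7 (optional, very minor)

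*SAP*

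**What the plan says.** Four SAP rules meet here.

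- **Intensity (4.4.2.1.1).** Daily records are "derived into daily intensity according to the following classification: None, Grade 1, Grade 2, Grade 3, or Missing". Missing is thus a category distinct from None. The note at the end of that section adds: "The maximum intensity on the ongoing period is derived from the record of the maximum intensity/measurement after the end of the solicited period", by the same rule. The post-D7 maximum can therefore also be Missing.
- **Ongoing (4.4.2.1.7).** Grade 1 or more is needed on both sides of the end of the solicited period. Otherwise: "In any other cases the reaction will not be considered as ongoing". The investigator's "ongoing flag is not used because the measurement would determine the ongoing status of the reaction".
- **Overall number of days (4.4.2.1.6).** The section opens with a condition: "If a reaction is ongoing at the end of the solicited period, then the overall number of days of occurrence is derived". Its inputs are the graded days within D0 to D7 and the date on which the reaction stopped. An incomplete stop date makes the result Missing. There is no matching rule for a missing intensity with a known stop date.
- **Missing intensities (5.3.1.4).** "For solicited reactions, missing intensities will be handled as described in" Section 4.4.2.1.1. That section turns blanks into None only if all daily records are missing and the investigator recorded presence as No, and fever is excepted.

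**The concern.** A missing post-D7 maximum gets the same answer as a recorded None, although other recorded data say the reaction continued. The reason given for setting the investigator's flag aside is that the measurement decides. That works for a recorded sub-threshold value, such as swelling under 25 mm. It does not work when there is no measurement.

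At stake are the derived ongoing status, which can be wrong in one direction only, and the overall number of days, which loses the part after D7 or has no defined value.

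**Working it through.** The documents give no figure to reproduce and no count of such records. The check is a reading of the rule plus its own day formula, applied to assumed subjects.

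**Step 1: which intensity pairs are affected.** Take D7 and the post-D7 maximum each as None, graded or Missing: 3 × 3 = 9 pairs.

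- Both recorded: 2 × 2 = 4 pairs. The rule works as intended.
- At least one Missing: 9 − 4 = 5 pairs, all not ongoing today.
- In 2 of these 5 the other value is None, which settles the answer as not ongoing.
- The remaining 3 are graded/Missing, Missing/graded and Missing/Missing.

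These are cells of a rule, not proportions of subjects. Only graded/Missing with a complete later stop date contradicts recorded data without depending on how the SAP is read.

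**Step 2: what the stop date shows in that case.** Pain, headache, malaise and myalgia are graded by the subject, and the lowest grade is presence without interference with activity (SAP Tables 4.1 and 4.2). If such a reaction is graded on D7 and stops later, it was at least Grade 1 after D7. Erythema, swelling and fever have a size or temperature threshold. Their stop date does not show whether they stayed at or above 25 mm or 38.0°C, so the status is unknown.

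**Step 3: the days not counted.** Inputs: the solicited period D0 to D07 has 8 days (SAP 4.3.2.3.2); S is the stop day counted from vaccination; n is the number of graded days in D0 to D7. The formula in 4.4.2.1.6 gives

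overall days = S + n − 8 + 1,

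so the excess over n is S − 7.

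Check with complete data: graded D5 to D7 (n = 3), post-D7 Grade 1, stop D10. Then 10 + 3 − 8 + 1 = 6, which is the span D5 to D10.

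If only the post-D7 maximum is made Missing, the reaction becomes not ongoing, the formula is not applied, and 3 days remain inside the solicited period.

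Pain graded on all of D0 to D7 (n = 8), post-D7 maximum Missing:

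| Stop day S | Formula | Overall days | Days within D0 to D7 |
|---|---|---|---|
| 8 | 8 + 8 − 8 + 1 | 9 | 8 |
| 12 | 12 + 8 − 8 + 1 | 13 | 8 |
| 30 | 30 + 8 − 8 + 1 | 31 | 8 |

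The formula needs no post-D7 grade. Only the ongoing condition keeps it from being used.

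**Step 4: a blank D7.** Pain D0 to D6 (n = 7), D7 blank, post-D7 Grade 1, stop D12: 12 + 7 − 8 + 1 = 12 if D7 was None, and 12 + 8 − 8 + 1 = 13 if it was graded. The records do not decide between them, so Missing is the right value.

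**The case against.** The best defence is that 4.4.2.1.7 is a deliberate, executable convention: a recorded grade is required on both sides of D7, identically in both arms. It fits its neighbours. In 4.4.2.1.4 a reaction counts as interrupted when it "reaction occurs over two separate periods of time intervened by at least one daily intensity Missing or None", and of the day count 4.4.2.1.5 says "It corresponds to the number of days with daily intensities of Grade 1, Grade 2, or Grade 3". Both treat a Missing day like None, and 5.3.1 allows no replacement of missing safety data. This explains reading a blank day as a gap. It does not explain setting aside a recorded stop date, and using that date fills in no intensity.

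The objection does stand on size. Diaries run until resolution (SAP 4.3.2.3.2) and are reviewed at Visit 2. Missing entries are clarified verbally (Protocol 13.2), and checks for omissions are applied (Protocol 11.2). The CRF is not among the documents, so it may not even accept a stop date with an empty maximum.

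Three stronger readings are tempting but not supported:

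- **A blank D7 wrongly overrides the stop date too.** This depends on whether the last daily intensity means D7 or the last recorded day, which the SAP does not say.
- **Reported durations are wrong.** The solicited endpoint in SAP 4.3.2.2 is days of occurrence up to 7 days, counted by 4.4.2.1.5. Table 5.2 lists duration without qualification, but in rows limited to 7 days after D0. No listed output clearly uses overall days.
- **Overall days are cut at D7.** The SAP gives no value for any not-ongoing reaction, even one with complete intensities. The D0 to D7 count is the natural reading, but it is an inference.

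**Conclusion.** The point holds narrowly. For a subject-graded reaction with D7 at least Grade 1, a Missing post-D7 maximum and a complete stop date after D7, the rule returns a status that the recorded data contradict, and the date goes unused. For measured reactions in the same position it returns a definite no where the answer is unknown.

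This is very minor and optional to correct. The safety analysis is descriptive, and nothing suggests a difference between arms. The size per subject is S − 7 days, if the overall number is taken as the D0 to D7 count. The number of subjects cannot be estimated from the documents and is probably very small. The conclusion assumes that the CRF permits this combination of entries.

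**What to change.** Add to SAP 4.4.2.1.7:

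*If the last daily intensity is at least Grade 1, the ongoing-period maximum is Missing and a complete stop date after D7 is recorded, then pain, headache, malaise or myalgia is considered ongoing and 4.4.2.1.6 applies. In any other case where an intensity needed for the decision is Missing and the other is not None, ongoing status and overall number of days are Missing.*

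Keep the present rule when both intensities are recorded or either is None. Leave 4.4.2.1.6 unchanged and do not bring in the investigator's flag.

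In programming, a post-D7 field should count as Missing only where an entry was due. A field left empty because the reaction had ended by D7 is not a missing intensity. The sponsor has to settle this against the CRF.

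The cost is two sentences in the SAP and one extra branch in the derivation program, with no new data. The drawback is that a few statuses and durations become Missing, and the tables need a place to show them.

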4.4.2.2 Unsolicited Non-serious AEs

4.4.2.2.1 Presence

An observation will be considered an event if it has at least a verbatim term and is not a Grade 0 intensity event. Grade 0 events should be included in the listing "Unsolicited non-serious AEs not included in the safety analysis."

4.4.2.2.2 Intensity

Intensity for unsolicited non-serious AEs will be derived according to the following classification: None, Grade 1, Grade 2, Grade 3, or Missing.

If the unsolicited non-serious AE is measurable and its preferred term is part of the list of solicited reactions, then the measurement is derived based upon and following the same rule as the intensity scales defined in the protocol for that measurable injection site or systemic reaction. Note the intensity could be considered "None" (not a reaction) in the analysis despite being considered a reaction by the investigator (e.g., swelling measurement > 0 mm but < 25 mm).

Intensity for the other unsolicited non-serious AEs will correspond to the value reported in the CRF.

The maximum intensity corresponds to the highest intensity for a unique term.

4.4.2.2.3 Last Vaccination

Last vaccination before any unsolicited non-serious AE is the study vaccination at V01.

4.4.2.2.4 Time of Onset

Time of onset is derived from the start date of the unsolicited non-serious AE provided in the clinical database and the date of last vaccination:

- start date of the unsolicited non-serious AE – date of previous vaccination

The time of onset should be considered as missing only if one or both of the dates are missing or partially missing.

The unsolicited non-serious AEs will be analyzed "Within 30 days", which corresponds to AEs with a time of onset between 0 and 30 days after vaccination or missing. An AE with missing time

of onset will be considered to have occurred just after the vaccination indicated by the visit number, so will be included in these tables.

Note: Unsolicited non-serious AEs that occurred before vaccination (negative time of onset) or with a time of onset higher than defined above will not be included in analysis, but will be listed separately.

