#### Blood sampling

All subjects will provide a pre-vaccination blood sample at Visit 1 and a post-vaccination sample at Visit 2 (30 to 44 days after the vaccination at Visit 1).

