#### **9.3.2.2 Safety Endpoints**

The observational endpoints for the evaluation of safety are:

- Occurrence, nature (Medical Dictionary for Regulatory Activities [MedDRA] preferred term), duration, intensity, and relationship to vaccination of any unsolicited systemic AEs reported in the 30 minutes after vaccination.
- Occurrence, time to onset, number of days of occurrence, intensity, action taken, and whether the reaction led to early termination from the study, of solicited (prelisted in the subject's DC and electronic case report form [CRF]) injection site reactions occurring up to 7 days after vaccination.
- Occurrence, time to onset, number of days of occurrence, intensity, action taken, and whether the reaction led to early termination from the study, of solicited (prelisted in the subject's DC and CRF) systemic reactions occurring up to 7 days after vaccination.
- Occurrence, nature (MedDRA preferred term), time to onset, duration, intensity, action taken, relationship to vaccination (for systemic AEs only), and whether the event led to early termination from the study, of unsolicited AEs occurring up to Visit 2.
- Occurrence, nature (MedDRA preferred term), time to onset, duration, seriousness criteria, relationship to vaccination, outcome, and whether the SAE led to early termination from the study, of SAEs throughout the trial.
- Occurrence, nature (MedDRA preferred term), time to onset, duration, seriousness, relationship to vaccination, and outcome for MAAEs from Visit 2 to the 6-month follow-up contact. MAAEs will be collected as unsolicited AEs up to Visit 2.

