4.3.2.2 Safety Endpoints

The observational endpoints for the evaluation of safety are:

- Occurrence, nature (Medical Dictionary for Regulatory Activities [MedDRA] preferred term), duration, intensity, and relationship to vaccination of any unsolicited systemic AEs reported in the 30 minutes after vaccination.
- Occurrence, time to onset, number of days of occurrence, intensity, action taken, and whether the reaction led to early termination from the study, of solicited (prelisted in the subject's DC and electronic case report form [CRF]) injection site reactions occurring up to 7 days after vaccination.
- Occurrence, time to onset, number of days of occurrence, intensity, action taken, and whether the reaction led to early termination from the study, of solicited (prelisted in the subject's DC and CRF) systemic reactions occurring up to 7 days after vaccination.
- Occurrence, nature (MedDRA preferred term), time to onset, duration, intensity, action taken, relationship to vaccination (for systemic AEs only), and whether the event led to early termination from the study, of unsolicited AEs occurring up to Visit 2.
- Occurrence, nature (MedDRA preferred term), time to onset, duration, seriousness criteria, relationship to vaccination, outcome, and whether the SAE led to early termination from the study, of SAEs throughout the trial.
- Occurrence, nature (MedDRA preferred term), time to onset, duration, seriousness, relationship to vaccination, and outcome for MAAEs from Visit 2 to the 6-month follow-up contact. MAAEs will be collected as unsolicited AEs up to Visit 2.

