4.3.2.3.3 Unsolicited Non-serious Adverse Events From Day 0 to Visit 2 After Vaccination

In addition to recording solicited reactions, subjects will be instructed to record any other medical events that may occur between Visit 1 and Visit 2 after vaccination. Space will be provided in the DC for this purpose.

For each unsolicited non-serious AE, the following information is to be recorded:

- Start and stop dates^a
- Intensity of the event:
 - For measurable unsolicited non-serious AEs that are part of the list of solicited reactions, the size of the AE as well as the temperature for fever will be collected and analyzed based on the corresponding scale used for solicited reactions (see [Table 4.1](#) and [Table 4.2](#)).
 - Other unsolicited non-serious AEs will be classified according to the following intensity scale:
 - Grade 1: No interference with activity
 - Grade 2: Some interference with activity
 - Grade 3: Significant; prevents daily activity
- Action taken for each AE, if any (e.g., medication)

The action taken by the subject to treat any **unsolicited AEs** will be classified in the CRF using the following scale:

- 0: None
- 1: Medication (self-medication with an existing prescription or over-the-counter medication)
- 2: Health care provider contact (no new medication prescribed)
- 3: Health care provider contact and prescription of a new medication (health care provider instructed subject to take a new medication, either an over-the-counter medication or one requiring a written prescription)

^a The stop date of all related AEs will be actively solicited. For other events, the investigator will provide the stop date when it becomes available. AEs for which no stop date was obtained during the course of the trial will be considered as ongoing at the end of the trial.

- Whether the AE led to discontinuation
- Whether the AE was related to vaccination (for unsolicited systemic AEs)

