5.1.3.1.3 For Safety Observational Objective

Safety results in [Section 4.3.2.2](#) will be described for subjects in all study groups. The main parameters for the safety endpoints will be described by 95% CIs (Clopper-Pearson method) (6). Analyses will contain at least the descriptions listed in [Table 5.2](#).

^a hSBA vaccine seroresponse for serogroups A, C, Y, and W is defined as:

- For a subject with a pre-vaccination titer $< 1:8$, the post-vaccination titer must be $\geq 1:16$.
- For a subject with a pre-vaccination titer $\geq 1:8$, the post-vaccination titer must be at least 4-fold greater than the pre-vaccination titer.

^b rSBA vaccine seroresponse is defined as a post-vaccination titer $\geq 1:32$ for subjects with pre-vaccination rSBA titer $< 1:8$, or a post-vaccination titer ≥ 4 times the pre-vaccination titer for subjects with pre-vaccination rSBA titer $\geq 1:8$.

Table 5.2: Statistical analyses for safety observational objective

Safety Events	Time and Group	Description
Immediate unsolicited systemic AE	Within 30 minutes after injection for all subjects in Groups 1 and 2 at D0	Proportion of subjects that have the event, MedDRA terms, intensity, relationship to vaccine, study discontinuation
Solicited injection site reactions	Up to 7 days after D0 for all subjects in Groups 1 and 2	Proportion of subjects that have the event, onset, duration, intensity, action taken, study discontinuation, temperature collection routes(if applicable)
Solicited systemic reactions	Up to 7 days after D0 for all subjects in Groups 1 and 2	
Unsolicited AE	Up to 30 days after D0 for all subjects in Groups 1 and 2	Proportion of subjects that have the event, MedDRA terms, onset, duration, intensity, relationship, action taken, study discontinuation
SAE	Up to 6-month follow-up after D0 for all subjects in Groups 1 and 2	Proportion of subjects that have the event, MedDRA terms, onset, duration, relationship, seriousness criteria, outcome, study discontinuation
MAAE	Between Visit 1 and Visit 2 for all subjects in Groups 1 and 2 (as unsolicited AE) From Visit 2 to 6-month follow-up for all subjects in Groups 1 and 2	Proportion of subjects that have the event, MedDRA terms, onset, duration, intensity, relationship, action taken, study discontinuation

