5.3.1.5 Start Date and Stop Date

Missing or partially missing start dates for unsolicited AEs will remain missing and not be imputed. If either the start or stop date is missing or partially missing, the time of onset will be considered to be missing. Nevertheless unsolicited AEs with missing time of onset will be included in analyses according to the visit collected.

Missing or partially missing stop dates for AEs (solicited reactions and unsolicited AEs) will remain missing and not be imputed.

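### SAP 5.3.1.5 and 4.4.2.2.4 define missing AE onset differently, and the unsolicited-AE tables stop at D30 while the endpoint runs to Visit 2 (D30 to D44)

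*SAP*

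**What the plan says.** **Missing onset.** SAP 4.4.2.2.4 subtracts the vaccination date from the AE start date and adds: "The time of onset should be considered as missing only if one or both of the dates are missing or partially missing". The dates meant are those two. An AE with missing onset is treated as having begun just after vaccination and goes into the 30-day table. SAP 5.3.1.5 gives a different rule: "If either the start or stop date is missing or partially missing, the time of onset will be considered to be missing". It keeps such AEs in the analyses. SAP 4.4.2.2.5 uses the stop date for duration. A footnote to SAP 4.3.2.3.3 regards an AE whose stop date was never obtained as ongoing at the end of the trial.

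**Window.** Protocol 9.3.2.2 defines the endpoint by several features "of unsolicited AEs occurring up to Visit 2", and SAP 4.3.2.2 repeats this. Protocol 5.1.3 has subjects give a "post-vaccination sample at Visit 2 (30 to 44 days after the vaccination at Visit 1"). SAP 4.3.2.3.3 tells subjects to record "any other medical events that may occur between Visit 1 and Visit 2 after vaccination". For analysis, however, SAP 4.4.2.2.4 tabulates onset from D0 to D30 or missing, and AEs "with a time of onset higher than defined above will not be included in analysis, but will be listed separately". The unsolicited-AE row of SAP Table 5.2 reads "Up to 30 days after D0 for all subjects in Groups 1 and 2" and does not mention missing onset.

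**The concern.** The first problem is a direct contradiction. Onset does not depend on when an AE ends, so the stop date has no place in deciding whether onset is known. A programmer who follows 5.3.1.5 discards a known onset and, because missing onset counts as within 30 days, can move an AE from the listing into the table. One who follows 4.4.2.2.4 does neither. The same data can therefore give two different unsolicited-AE tables, both produced according to the SAP.

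The second problem is a mismatch between endpoint and output. Non-serious AEs dated from D31 to Visit 2 belong to the endpoint as worded and are collected, but no unsolicited-AE table contains them. The length of the omitted part depends on when each subject happened to attend Visit 2.

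At stake is whether the descriptive unsolicited-AE tables correspond to their endpoint and can be reproduced. The primary immunogenicity comparison is not touched.

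**Working it through.** The plan states no figure on this point, so there is none to reproduce. Two checks apply.

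**1. Test AEs under the two missing-onset rules.** Under 4.4.2.2.4, onset = start day, with vaccination on D0, and is missing only if the start or vaccination date is missing or partial. Under 5.3.1.5 it is also missing if the stop date is missing or partial. In both cases an AE is tabulated if onset is 0 to 30 or missing, and otherwise only listed. The vaccination date is taken as known.

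| Start | Stop | 4.4.2.2.4 | 5.3.1.5 |
|---|---|---|---|
| D10 | D15 | onset 10, tabulated | onset 10, tabulated |
| D10 | missing or partial | onset 10, tabulated | onset missing, tabulated |
| D35 | D40 | onset 35, listed only | onset 35, listed only |
| D35 | missing or partial | onset 35, listed only | onset missing, tabulated |
| D-2 | D3 | onset -2, listed only | onset -2, listed only |
| D-2 | missing or partial | onset -2, listed only | onset missing, tabulated |

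The rules agree whenever both dates are complete. With an incomplete stop date, the D35 AE and the AE that began before vaccination change placement. The D10 AE stays in the table but loses its known onset. A partial stop date is enough to produce this. Whether an ongoing AE also counts as having a missing stop date is not stated.

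**2. Collection days outside the D0 to D30 tables.** Inputs: Visit 2 on D30 to D44 (Protocol 5.1.3; SAP 3.2), collection from D0 to Visit 2 (SAP 4.3.2.3.3), analysis from D0 to D30 (SAP 4.4.2.2.4), all counted inclusively. Let d = Visit 2 day - 30. D0 to D30 is 31 days, so collection lasts 31 + d days and the share outside is d/(31 + d):

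- Visit 2 on D30: 0/31 = 0%
- Visit 2 on D33: 3/34 = 8.8%
- Visit 2 on D37: 7/38 = 18.4%
- Visit 2 on D44: 14/45 = 31.1%

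These are shares of time. For a share of events, assume that the daily onset rate after D30 is r times the rate in D0 to D30. The share is then r·d/(31 + r·d):

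- D37: 18.4% for r = 1; 3.5/34.5 = 10.1% for r = 0.5; 1.75/32.75 = 5.3% for r = 0.25
- D44: 31.1% for r = 1; 7/38 = 18.4% for r = 0.5; 3.5/34.5 = 10.1% for r = 0.25

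The documents give neither the distribution of Visit 2 dates nor AE rates, so the values of r and the days chosen are illustrative.

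**The case against.** The best defence of the window is that 30 days was intended. Protocol 9.3.2.3.3 is headed and worded for 30 days. The text below Protocol Table 5.1 and SAP Table 3.1 equates D30 with Visit 2, and Protocol 6.7 gives a 30-day safety follow-up as its example. On that reading, Visit 2 in the endpoint means its nominal day and the 14 days are a scheduling allowance. A fixed window also gives every followed subject the same risk period, which a table to Visit 2 would not. Most of this stands. The documents are split, and a reader who infers that the SAP simply departs from an unambiguous protocol goes further than the text allows. Against a settled 30-day intention, SAP 4.3.2.3.3 extends to Visit 2 the recording period that the protocol's matching section gives as 30 days, while the analysis rule stays at D30.

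Three other stronger readings are tempting but not supported:

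- **That late AEs disappear from the report.** They are listed. Early terminations for an AE are counted in the disposition table (SAP 4.4.2.5.6). AEs with action taken 2 or 3 may appear as MAAEs between Visit 1 and Visit 2. That last route is not certain, because SAP 4.4.2.4 borrows the calculation methods of 4.4.2.2, which contain the D30 limit.
- **That MAAEs after D30 are dropped.** SAP 4.4.2.4, 4.4.4.4 and Table 5.2 give explicit MAAE periods, so this is probably not meant. It needs a clarifying sentence and is not a separate defect.
- **That unresolved AEs will certainly enter the 30-day table under 5.3.1.5.** This follows only if ongoing counts as a missing stop date.

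On missing onset, the defence is that 5.3.1.5 looks like a drafting slip, given the formula and the restrictive wording of 4.4.2.2.4. That is likely, but the sentence still has to be corrected before it is programmed.

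**Conclusion.** Both parts hold, and the missing-onset conflict is the clearer one. SAP 5.3.1.5 and 4.4.2.2.4 cannot both be followed for an AE with a known start and an incomplete stop date. The choice decides whether an AE dated after D30 or before vaccination enters the 30-day table. Its frequency cannot be estimated from the documents.

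On the window, the endpoint as worded has no matching table for dated non-serious AEs from D31 to Visit 2. The gap is 0 to 14 days per subject, or 0% to 31.1% of collection time. The upper figure needs a D44 visit, and it would be a share of events only if the onset rate did not fall after D30.

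The consequence is minor to moderate. The D30 cut-off removes no SAE, because SAP 4.4.2.3.2 also analyses SAEs over the whole study. The rule is the same in both groups, and safety is descriptive. The SAP contents lists a section 5.7 on changes to planned analyses that is not in the text available, so whether it explains the 30-day window cannot be checked. Both points should be settled before database lock.

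**What to change.** - **SAP 5.3.1.5:** define missing onset by the start or vaccination date only, in line with 4.4.2.2.4. Let a missing or partial stop date affect duration alone, as 4.4.2.2.5 already provides. State whether an ongoing AE counts as having a missing stop date.
- **SAP 4.4.2.2.4 and Table 5.2:** keep the fixed D0 to D30 table and add a D31-to-Visit 2 row or a D0-to-Visit 2 summary. SAP 4.4.2.3.2 already uses this two-period pattern for SAEs. If 30 days was intended, restate the endpoint as D0 to D30 in both documents instead.
- **Protocol 9.3.2.3.3:** reconcile its 30-day recording period with the endpoint, whichever window is chosen.
- **SAP 4.4.2.4 (clarification):** say that the cross-reference to 4.4.2.2 covers the derivation formulas, and that MAAEs are analysed over the two periods in Table 5.2 without the D30 limit.

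The cost is a few lines of text and at most one table or row. No new data are needed, because the diary card already runs to Visit 2. The one drawback of a summary to Visit 2 is unequal follow-up between subjects (to D30 for some and D44 for others), which is why the fixed 30-day table should stay beside it.
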